#### 13.3.2.1. The Pittsburgh Sleep Quality Index (PSQI)

Observed and change from Baseline values for the overall and component scores of the PSQI are to be summarised by descriptive statistics (n, mean, SD, median, minimum and maximum) for each annual Allergy Assessment Period and treatment arm.

#### 13.3.2.2. 6-Question Asthma Control Questionnaire (ACQ) Score

Observed and change from Baseline values for the ACQ score are to be summarised by descriptive statistics (n, mean, SD, median, minimum and maximum) for each annual Allergy Assessment Period and treatment arm for subjects with a history of asthma as assessed at the Screening visit of the CP007 study.

#### 13.3.2.3. Work Productivity and Activity Impairment Questionnaire plus Classroom Impairment Questions: Allergy Specific (WPAI:CIQ-AS)

Observed values for the seven WPAI:CIQ-AS component scores are to be summarised by descriptive statistics (n, mean, SD, median, minimum and maximum) for each annual Allergy Assessment Period and treatment arm.

The number and percentage of subjects that are either currently working (question 1) or currently students (question 5) are to be presented. The denominator for the percentages is the total number of subjects in the population treatment arm with data available.

---

Document: CP007A SAP.docx

Author: [name]

Version Number:

V 2.0

Version Date:

23 Feb 2017

Template No: CS\_TP\_BS016 – Revision 3

Reference: CS\_WI\_BS005

Effective Date: 01May2012

Copyright © 2012 Quintiles Transnational Corp. All rights reserved.

The contents of this document are confidential and proprietary to Quintiles Transnational Corp. Unauthorized use, disclosure or reproduction is strictly prohibited.

#### 13.3.2.4. Environmental Changes and Global Assessment of Symptom Severity

The number and percentage of subjects that answer “Yes” or “No” to each home environment question and fall within each of the symptom severity categories are to be presented for each monthly assessment and treatment arm.

The percentages for global assessment of symptom severity categories are to be calculated relative to the number of subjects in the relevant population that answered “Yes” to “Have you been to a house in the last month where there is a cat?” at each month.

A p-value for the difference in global assessment of symptom severity between treatment arms is to be calculated using the Cochran-Mantel-Haenszel (CMH) row mean score difference for all subjects that no longer keep a cat and presented for each treatment arm vs. Placebo.

#### 13.3.2.5. Monthly Days Off School/Work

The number of days that either school or work was missed due to allergic Rhinoconjunctivitis symptoms is to be summarised by descriptive statistics (n, mean, SD, median, minimum and maximum) for each month and treatment arm.

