7.4.2.2.5 Medical Visits

An evaluation of additional visits to doctors/clinics will be performed.

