7.4.2.3.3 Health Economic Outcomes

Health economic outcomes will be described and explored.

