### 2.3. EXPLORATORY OBJECTIVES

The exploratory objectives are:

- To evaluate the effect of Cat-PAD on changes in asthma control in asthmatic subjects for up to 5 years after the administration of treatment.
- To evaluate the effect of Cat-PAD on changes in sleep quality in adults using the Pittsburg Sleep Quality Index (PSQI) for up to 5 years after the administration of treatment.
- To evaluate the effect of Cat-PAD on changes in productivity using the Work Productivity and Activity Impairment Questionnaire plus Classroom Impairment Questions: Allergy Specific (WPAI:CIQ-AS) for up to 5 years after the administration of treatment.
- To evaluate the effect of Cat-PAD on symptomatology on unplanned exposure to a cat in normal daily life in subjects who no longer keep a cat for up to 5 years after the administration of treatment.
- To evaluate the effect of Cat-PAD on health economic outcomes for up to 5 years after the administration of treatment.

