#### 13.3.1.5. Monthly Days Off School/Work

On a monthly basis subjects will enter in their dairy binders the total number of days that either school or work was missed due to allergic Rhinoconjunctivitis symptoms during the past month.

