#### 13.3.2.6. Hospital/Doctor Office Visits

The total number of hospitalisations as well as the number and percentage of subjects hospitalised are to be presented for each monthly assessment and treatment arm.

The length of stay of visits is to be summarised by descriptive statistics (n, mean, SD, median, minimum and maximum) for each monthly assessment and treatment arm.

Similarly, the total number of doctor visits as well as the number and percentage of subjects with any visit to the doctor are to be presented for each monthly assessment and treatment arm.

---

Document: CP007A SAP.docx

Author: [name]

Version Number:

V 2.0

Version Date:

23 Feb 2017

Template No: CS\_TP\_BS016 – Revision 3

Reference: CS\_WI\_BS005

Effective Date: 01May2012

Copyright © 2012 Quintiles Transnational Corp. All rights reserved.

The contents of this document are confidential and proprietary to Quintiles Transnational Corp. Unauthorized use, disclosure or reproduction is strictly prohibited.

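### Lost work/school days, doctor visits and hospitalisations are summarised only month by month, so the exploratory health-economic objective gets no yearly per-subject figure and no estimate of a treatment effect

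*SAP*

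**What the plan says.** The objective is in SAP section 2.3: "To evaluate the effect of Cat-PAD on health economic outcomes for up to 5 years after the administration of treatment". Protocol section 2.3 has the same objective.

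The planned analyses are these:

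- **Lost work/school days.** Section 13.3.1.5 has each subject enter "the total number of days that either school or work was missed due to allergic Rhinoconjunctivitis symptoms during the past month". Section 13.3.2.5 says this count "is to be summarised by descriptive statistics (n, mean, SD, median, minimum and maximum) for each month and treatment arm".
- **Hospitalisations.** Section 13.3.2.6 gives the total, and the "number and percentage of subjects hospitalised are to be presented for each monthly assessment and treatment arm".
- **Length of stay.** Same section: "The length of stay of visits is to be summarised by descriptive statistics", again by monthly assessment and arm.
- **Doctor visits.** Same section: the total and the number and percentage of subjects with any visit "are to be presented for each monthly assessment and treatment arm".

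SAP Appendix 1 (Presentation of Visits) labels the monthly assessments 01 to 12. That is 12 summaries per outcome for each year analysed, and at most 12 × 4 = 48. Fewer result if the later years are not analysed, because SAP section 4 makes each later year depend on a positive outcome before it.

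The protocol's own commitment on analysis is modest. Section 7.4.2.3.3 reads "Health economic outcomes will be described and explored". Section 7.4.2.2.5 adds "An evaluation of additional visits to doctors/clinics will be performed"; it stands under Secondary Analysis, although section 3.2.3 lists visits as exploratory.

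**The concern.** These outcomes are collected as monthly counts, many of them probably zero, and they could be added up per subject over the year. The SAP never does so, and it plans no difference or ratio between arms with a confidence interval. A reader of the outputs would have to judge a treatment effect by eye across 12 separate monthly summaries per outcome.

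The SAP does not rule out comparisons for exploratory outcomes: section 13.3.2.4 plans a CMH p-value against placebo for the global symptom assessment. The protocol synopsis also foresees confidence intervals for differences between groups where appropriate.

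A second issue concerns unreturned diaries. Visits and hospitalisations are reported as raw totals. Anyone who adds these totals over 12 months to obtain a yearly figure counts each unreturned month as zero events. The SAP gives no rule for this. Section 7.3 refers missing efficacy data to section 13.1.3, which deals only with the daily Combined Score.

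At stake is the usefulness of one exploratory objective, on data that are already being collected.

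**Working it through.** **No figure to reproduce.** The documents give no event rate, SD, effect size or power for lost days, visits or stays. The power statements in protocol section 7.2 concern the Combined Score and have no bearing here. What follows is an illustration.

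**Inputs.** 130 subjects per arm (protocol section 7.2, the number after attrition). Assumed: 0.05 to 0.3 events per subject-month, and variance = mean + k × mean² with k from 0.5 to 2.

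**Formula.** With m = monthly rate × months, the relative variance per subject is (m + k m²)/m² = 1/m + k. The SE of the log rate ratio between two arms is √(2 × (1/m + k)/130).

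| Rate per month | k | 1/m + k, one month | SE, one month | 1/m + k, 12 months | SE, 12 months | Ratio of SEs |
|---|---|---|---|---|---|---|
| 0.05 | 0.5 | 20.5 | 0.56 | 2.17 | 0.18 | 3.08 |
| 0.05 | 2 | 22.0 | 0.58 | 3.67 | 0.24 | 2.45 |
| 0.1 | 1 | 11.0 | 0.41 | 1.83 | 0.17 | 2.45 |
| 0.3 | 0.5 | 3.83 | 0.24 | 0.78 | 0.11 | 2.22 |
| 0.3 | 2 | 5.33 | 0.29 | 2.28 | 0.19 | 1.53 |

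The one-month SE runs from 0.24 to 0.58 and the yearly SE from 0.11 to 0.24; one month is about 1.5 to 3.1 times less precise. At 266 per arm every SE falls by √(266/130) = 1.43 and the ratios do not change. The formula treats each subject's underlying rate as constant over the year. Extra month-specific variation would favour the yearly figure further.

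**Monthly medians.** Under the matching negative binomial, the share of subjects with no event in a month is (1 + k m)^(−1/k). This is (1.15)^(−2) = 0.76 at rate 0.3 with k = 0.5, and (1.1)^(−1/2) = 0.95 at rate 0.05 with k = 2. Under these assumptions every monthly median is 0.

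**Cross-check by another route.** For 12 equally correlated months, the SE of the yearly mean relative to one month is √((1 + 11ρ)/12): 0.42 at ρ = 0.1, 0.60 at 0.3, 0.74 at 0.5 and 0.90 at 0.8. The yearly summary is more precise for any ρ below 1. The size of the gain depends on a correlation that the documents do not give.

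**Hospitalisations separately.** The lowest rate above, 0.05 × 12 = 0.6 a year, is likely too high for hospital admissions. At assumed rates of 2% and 5% a year and 130 per arm:

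- Expected events per arm per month are 130 × 0.02/12 = 0.22 and 130 × 0.05/12 = 0.54. The Poisson chance of an empty monthly cell is e^(−0.22) = 81% and e^(−0.54) = 58%.
- Expected events per arm over the year are 2.6 and 6.5. With k = 1, the yearly SE is √(2 × 51/130) = 0.89 and √(2 × 21/130) = 0.57. The 95% CI extends by a factor of about 5.7 and 3.0 each way.

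Yearly aggregation therefore gives a more readable table for hospitalisations, but a fitted rate ratio would say little.

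**The case against.** The strongest reply is that description is what the protocol planned. The endpoints are exploratory, section 7.4.2.3.3 promises no estimate, and section 7.4.2.3 leaves the method open. This stands. A reader might infer from the word effect in the objective that a promised comparison has been dropped, but the documents do not support that. The gap lies between the wording of the objective and tables that estimate nothing.

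Other points that stand:

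- A reader might picture 12 separate tables a year. Appendix 1 gives only month labels, and one table can hold 12 rows.
- A reader might extend the missing-as-zero problem to lost days. Section 13.3.2.5 reports n and mean each month, so the mean is over subjects with data. Adding the monthly means gives an arm-level yearly figure that does not count missing months as zero, though it has no CI. The problem is confined to raw totals of visits and hospitalisations.
- A reader might conclude that a yearly model would reveal effects in all these outcomes. For hospital stays the figures above do not support it.
- One model for every outcome would be wrong. Subjects who neither work nor study cannot lose such days, a distinction that SAP section 13.3.2.3 recognises by tabulating both statuses. Length of stay is not an event count.

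Two further replies carry less weight. SAP section 1 refers to output shells that are not supplied, so a yearly total row cannot be excluded; it would still not provide a between-arm estimate. Appendix 1 requires a denominator other than the population count to be identified, or the denominator footnoted; this helps with the percentages but not the raw totals. The annual WPAI:CIQ-AS does not fill the gap: it serves a separate productivity objective, its missed-time items cover seven days, and it too is only described.

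**Conclusion.** The point holds as a minor, cheap improvement. For lost days, doctor visits and hospitalisations, the SAP plans month-by-arm summaries only, with no yearly per-subject figure and no between-arm estimate. Neither document lists which variables make up the health economic outcomes. The SAP has no section of its own for them, and these are the natural candidates.

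For doctor visits and lost days, the loss of precision is a factor of about 1.5 to 3.1, resting wholly on the assumed rates and over-dispersion. That range should not be applied to hospitalisations. No promised test is breached, and no primary conclusion is affected.

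**What to change.** For each analysis year, derive for each subject the total for each count outcome and the number of monthly diaries returned, and report the rate per subject-year by arm. Then:

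- **Doctor visits and lost days:** add a rate ratio against placebo with 95% CI for each regimen, labelled exploratory. One suitable model is a negative binomial with log months reported as offset.
- **Lost days:** restrict this analysis to subjects who are working or studying. The SAP should state how the once-a-year status answers (WPAI:CIQ-AS questions 1 and 5) are applied to the monthly diaries.
- **Hospitalisations:** report the yearly count and rate by arm with a CI, and fit no model if events are few.
- **Length of stay:** summarise descriptively over the year.

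Keep the monthly summaries. The data are already collected, so subjects carry no extra burden. The cost is one short derivation, two exploratory models and a little more programming for each year analysed.

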#### 13.3.2.6. Hospital/Doctor Office Visits

The total number of hospitalisations as well as the number and percentage of subjects hospitalised are to be presented for each monthly assessment and treatment arm.

The length of stay of visits is to be summarised by descriptive statistics (n, mean, SD, median, minimum and maximum) for each monthly assessment and treatment arm.

Similarly, the total number of doctor visits as well as the number and percentage of subjects with any visit to the doctor are to be presented for each monthly assessment and treatment arm.

---

Document: CP007A SAP.docx

Author: [name]

Version Number:

V 2.0

Version Date:

23 Feb 2017

Template No: CS\_TP\_BS016 – Revision 3

Reference: CS\_WI\_BS005

Effective Date: 01May2012

Copyright © 2012 Quintiles Transnational Corp. All rights reserved.

The contents of this document are confidential and proprietary to Quintiles Transnational Corp. Unauthorized use, disclosure or reproduction is strictly prohibited.

## 14. SAFETY OUTCOMES

All outputs for AEs are to be based on the Safety population.

There are to be no statistical comparisons between the treatment arms for safety data, unless otherwise specified with the relevant section.

### 14.1. ADVERSE EVENTS

AEs are to be coded using the Medical Dictionary for Regulatory Activities (MedDRA) Version 19.0.

AE reporting begins from signed informed consent and ends when the subject completes the study or withdraws.

An AE is any untoward medical occurrence. An AE can therefore be any unfavourable and unintended sign, symptom or disease.

An overall summary of number of subjects (n), percentage of subjects (%) and total number of mentions (m) within each of the following categories is to be presented:

- Any AE
- Any AE by maximum severity
- Any AE by strongest relationship
- Any AE leading to premature withdrawal from the study
- Any serious AE
- Any AE leading to death

Listings will include all AEs.

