7.2 Sample Size

Subjects who were randomised in clinical study CP007 and completed PAC3 will be eligible for entry into this study, hence no formal sample size calculation has been performed.

A sample size of 266 evaluable subjects per arm will have at least 99% power to detect a 25% treatment difference in the mean CS during the PAC3 period between each of the Cat-PAD treatment groups and placebo. This is based on subjects in the placebo treatment group having a CS (0-6) of 2.10 which relates to a 25% Cat-PAD mean CS treatment difference of 0.525, with a common within-group standard deviation (SD) of 1.29 (i.e. the same assumptions as for CP007). Note: A treatment effect of 20% greater than placebo is considered clinically relevant because it exceeds the treatment effect of leukotriene receptor antagonists, antihistamines and intranasal corticosteroids (Wilson et al, 2004.) This power calculation is based on a Bonferroni-Holm adjusted alpha of 0.025 for the primary analysis given there will be two comparisons

(two courses of Cat-PAD versus placebo and one course of Cat-PAD versus placebo) with the tests assumed to be two sided.

It is recognised that some subjects will withdraw from the study before the end of the four year period but it will still have at least 80% power to detect a difference between active treatment and placebo with 130 subjects per arm.

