The annual Allergy Evaluation Period for CO007A is defined as a 3-week (21 day) period, taking place at the same time of year as the 3-week Baseline Allergy Evaluation visit in CP007 (Visits 2A and 2B) and is to include:

- At the start of the 3-week Allergy Evaluation Period
  - o Diagnosis of asthma
- Daily recording for 3 weeks
  - o Rhinoconjunctivitis symptoms
  - o Asthma symptoms
  - o Allergy medication use
  - o Exposure to indoor cat
- At the end of the 3-week Allergy Evaluation Period
  - o Change in geographic location
  - o 6-Question asthma control questionnaire (ACQ) excluding lung function (for asthmatics only)
  - o RQLQ
  - o PSQI (if at least 18 years old at the time of assessment)
  - o WPAI:CIQ-AS

Subjects are to have up to four study visits each year, two of which may be conducted by telephone. At each visit, site staff will record any AEs and SAEs, and at the on-site visits subjects are to be provided with their next diary binder.

Subjects will have a final End of Study Visit, which will coincide with the end of the final annual Allergy Evaluation Period assessment.

The duration of this follow-up study is to be up to 4 years for each subject.

---

Document: CP007A SAP.docx  
Author: [name]

Version Number: V 2.0  
Version Date: 23 Feb 2017

Template No: CS\_TP\_BS016 – Revision 3  
Effective Date: 01May2012

Reference: CS\_WI\_BS005

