### 4.1. FINAL ANALYSES

All final, planned analyses identified in this SAP are to be performed by Quintiles Biostatistics.

The following events are prerequisites for the production of any of the four interim analyses planned.

- Sponsor authorisation of the SAP and Table, Listing, Figure (TLF) shells
- Quintiles authorisation of final locked database snapshot

---

Document: CP007A SAP.docx  
Author: [name]

Version Number: V 2.0  
Version Date: 23 Feb 2017

Template No: CS\_TP\_BS016 – Revision 3  
Effective Date: 01May2012

Reference: CS\_WI\_BS005

For each interim analysis Quintiles Biostatistics will extract all data as entered in the relevant year's diary binder of each subject (there is a separate diary binder for each analysis year).

After cleaning (no outstanding data queries) of the relevant analysis year's data by DataMatica and authorisation by Quintiles Biostatistics as well as coding of all AEs and concomitant medications by Quintiles Coding, the final locked database snapshot for the relevant interim analysis (year 1, year 2, year 3 or year 4) is to be provided by DataMatica to Quintiles for the purpose of producing the interim analysis.

AEs entered in the Adverse Event Case Report Form (CRF) are to be cumulative and will not be assigned to a specific year for analysis.

- Sponsor authorisation of analysis sets

Prior to each interim analysis Quintiles Biostatistics will programmatically prepare listings of all subjects and their status with regards to inclusion or exclusion from each analysis population based on the definitions of each analysis population as described in [Section 5: Analysis Sets](#).

The listings are to be provided to Circassia for authorisation prior to each interim analysis.

---

Document: CP007A SAP.docx

Author: [name]

Version Number:

V 2.0

Version Date:

23 Feb 2017

Template No: CS\_TP\_BS016 – Revision 3

Reference: CS\_WI\_BS005

Effective Date: 01May2012

Copyright © 2012 Quintiles Transnational Corp. All rights reserved.

The contents of this document are confidential and proprietary to Quintiles Transnational Corp. Unauthorized use, disclosure or reproduction is strictly prohibited.

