### 5.4. SAFETY POPULATION [SAF]

All subjects are to be included in the safety population. Safety data is to be listed and summarised by study medication actually received in study CP007.

---

Document: CP007A SAP.docx  
Author: [name]

Version Number: V 2.0  
Version Date: 23 Feb 2017

Template No: CS\_TP\_BS016 – Revision 3  
Effective Date: 01May2012

Reference: CS\_WI\_BS005

Copyright © 2012 Quintiles Transnational Corp. All rights reserved.

The contents of this document are confidential and proprietary to Quintiles Transnational Corp. Unauthorized use, disclosure or reproduction is strictly prohibited.

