#### 14.1.2. AEs LEADING TO WITHDRAWAL FROM STUDY

AEs leading to withdrawal from the study are to be identified on the Adverse Events CRF as events with an action taken of “Subject withdrawn because of this event”.

For AEs leading to withdrawal from study, summaries of incidence rates (frequencies and percentages) by SOC and PT are to be presented.

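### AE tables give crude percentages and counts over up to four years with no observation time by arm, so any difference in retention between arms cannot be separated from a difference in AE risk

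*SAP*

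**What the plan says.** **Metric.** The overall AE summary in SAP 14.1 gives "number of subjects (n), percentage of subjects (%) and total number of mentions (m"). SAP 14.1.1 breaks incidence down by SOC and PT, and by severity and relationship. For AEs leading to withdrawal, SAP 14.1.2 says "summaries of incidence rates (frequencies and percentages) by SOC and PT are to be presented", so a rate here means a percentage of subjects.

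**Window.** SAP 14.1 states that "AE reporting begins from signed informed consent and ends when the subject completes the study or withdraws". SAP 3.1 adds: "The duration of this follow-up study is to be up to 4 years for each subject". Observation time therefore varies between subjects.

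**Pooling over years.** SAP 4.1 says that AEs from the case report form "are to be cumulative and will not be assigned to a specific year for analysis".

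**Denominator.** SAP 5.4: "All subjects are to be included in the safety population". A subject seen for two months counts the same as one seen for four years.

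**Withdrawals.** Protocol 7.2: "It is recognised that some subjects will withdraw from the study before the end of the four year period". It gives no rate, overall or by arm. SAP 9 tabulates premature withdrawals and reasons, but not length of follow-up.

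**Comparison.** Continued safety and tolerability is a secondary objective (Protocol 2.2, SAP 2.2). Protocol 7.4.3 plans descriptive AE differences between each treatment group and placebo, without tests. SAP 14 rules out statistical comparison of safety data unless otherwise specified.

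Neither document mentions subject-years, rates adjusted for observation time, time-to-event AE summaries or a table of follow-up duration by arm.

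**The concern.** A cumulative percentage depends on the event rate and on how long subjects are watched. A count of mentions is proportional to total observation time. When observation is long and can end early, the two quantities compare arms fairly only if follow-up is similarly distributed in each arm.

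That could fail in either direction. If placebo subjects leave sooner because their symptoms persist, the active arms accumulate more AEs at an identical rate and look less safe. If the active arms lose subjects faster, a real excess is diluted. Without observation time in the tables, a reader of the long-term safety results cannot tell which has happened.

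A separate, smaller matter concerns the yearly analyses. SAP 4 waits until every subject has completed, left before or passed the relevant annual assessment. Subjects who are already further on bring extra AE time, because events are not tied to a year. A year 1 AE table therefore mixes different lengths of observation and is hard to set against a year 2 table.

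**Working it through.** **The plan's own figures.** The documents give no AE rate. The only stated figures that can be recomputed are the power statements in Protocol 7.2 (difference 0.525, SD 1.29, two-sided alpha 0.025). With 266 per arm I get 99.3%, against a stated minimum of 99%. With 130 per arm I get 85.1%, against a stated minimum of 80%. Both reproduce. They do not enter the AE argument, except that 130/266 = 48.9% suggested the lower retention value of 49% in the second table. It is not a forecast of retention.

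**Assumptions, none of them from the documents.** A constant AE hazard h, the same in both arms; exponential dropout; four-year retention R.

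**Formulae**, with T = 4 years:
- dropout hazard d = −ln(R)/4
- crude proportion with an event = h/(h + d) × [1 − exp(−4(h + d))]
- mean follow-up = [1 − exp(−4d)]/d = (1 − R)/d
- expected mentions = N × h × mean follow-up, so the ratio of mentions equals the ratio of mean follow-up

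**Retention 58% versus 48%.** d = 0.1362 and 0.1835 per year. Mean follow-up is 0.42/0.1362 = 3.08 years and 0.52/0.1835 = 2.83 years, a ratio of 1.09.

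Worked case, h = 0.3:
- 58% retained: 0.3/0.4362 × [1 − exp(−1.745)] = 56.8%
- 48% retained: 0.3/0.4835 × [1 − exp(−1.934)] = 53.1%

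| h per year | 58% retained | 48% retained | artefact, points |
|---|---|---|---|
| 0.02 | 6.0% | 5.5% | 0.5 |
| 0.05 | 14.1% | 13.0% | 1.1 |
| 0.1 | 25.9% | 23.9% | 2.0 |
| 0.3 | 56.8% | 53.1% | 3.7 |
| 1.0 | 87.1% | 83.8% | 3.3 |

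**Wider gap, 80% versus 49%.** Mean follow-up is 3.59 and 2.86 years, a ratio of 1.25.

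| h per year | 80% retained | 49% retained | ratio |
|---|---|---|---|
| 0.02 | 6.9% | 5.5% | 1.25 |
| 0.05 | 16.3% | 13.1% | 1.24 |
| 0.2 | 50.1% | 41.2% | 1.22 |
| 1.0 | 93.3% | 84.1% | 1.11 |

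At h = 0.05 and 266 per arm, expected mentions are 266 × 0.05 × 3.59 ≈ 48 and 266 × 0.05 × 2.86 ≈ 38. Dividing by subject-years returns 5.0 per 100 in both arms. A simulation of 1,000,000 subjects per arm gave first-event rates of 5.00 and 4.99, so the spurious difference disappears.

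**Equal retention, 49% versus 49%.** The ratio is 1.00 at every hazard, so there is no bias.

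**Pattern.** For uncommon events the ratio of percentages is close to the follow-up ratio, but the gap in points is small. For very common events the ratio shrinks because nearly everyone has an event.

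**The case against.** The strongest reply is that a bias between arms needs a premise that the documents do not supply. They say only that some subjects will withdraw. Equal retention removes the problem, and a gap could run either way. This stands, and it makes the point conditional.

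Staggered entry gives no reason for one arm to look less safe. Arms were randomised in CP007, and nothing suggests that entry time differs by arm. This also stands. What remains is that each yearly table mixes lengths of observation.

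Safety is descriptive and untested, so no inferential result is distorted. That is right, but Protocol 7.4.3 still puts differences from placebo before the reader, and those differences are what retention can move.

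Some of the information exists elsewhere. Withdrawals and reasons are tabulated, AEs are classified by relationship to the CP007 medication, listings carry study day, and each analysis uses a locked snapshot. These help someone prepared to work from listings. They do not put observation time into the summary tables, and a snapshot does not align events with time at risk.

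Finally, SAP 14.1.2 says in the same phrase what its incidence rates are, so the label misleads little. The gap is the missing denominator rather than the word.

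**Conclusion.** The point holds as a conditional weakness in presentation. The planned AE tables cannot show whether a difference between arms reflects risk or length of observation.

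Its size depends wholly on assumed retention and hazards. With 58% versus 48% retained at four years it runs from about 0.5 to 3.7 percentage points over hazards of 0.02 to 1.0 per year. With 80% versus 49% the ratio of percentages is about 1.1 to 1.25. Both are four-year figures under exponential dropout and equal constant hazards. SAP 4 runs the later yearly analyses only after positive earlier ones, so four years is the longest case.

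A reader might infer that the active arms will look less safe than they are. The documents do not support that: they give no withdrawal rate by arm and no direction, and with equal follow-up the bias is nil. Nor do they support the reading that staggered enrolment biases the comparison between arms. Type I error is not affected. This is an inexpensive improvement and does not invalidate the safety analysis.

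**What to change.** In SAP 14.1, keep n, % and m and add beside them:

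1. Subject-years of observation by arm.
2. Observation-time-adjusted rates per 100 subject-years for any AE, SAEs, AEs leading to withdrawal and AEs by SOC and PT. State whether each rate counts first events (time to first event as denominator) or all events (total time as denominator). Refer to observation time rather than exposure, since no product is given in this study.
3. An AE cut-off for each yearly analysis, applied to both events and time at risk so that they match.
4. A rule for the end of time at risk: the completion or withdrawal visit date or, for subjects lost without that visit, the last recorded contact.

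The main dates are already collected: consent (SAP 6.1), AE start and stop (Protocol 6.4.1), and completion or withdrawal visit (Protocol 6.2.4). The cost is a few table columns and the programming of the cut-off. The downside is that a single rate summarises the data well only if the hazard is roughly constant, which is why the rates should accompany the percentages and not replace them.
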